### 1.3. Study Design

#### Overview of Study Design and Key Characteristics

	
Design Features	
 
This is a multi-center, randomized, open-label, blinded evaluation endpoint, and parallel controlled clinical study. The study contents include: 1) Screening and baseline period: Confirm whether the patients are eligible for the study and make a record and decide whether trepanation and drainage should be performed by considering the condition of the disease and the imaging results, and then carry out randomization and therapy. Eligible subjects will be randomly assigned to the traditional treatment group or MMA embolization group at the ratio of 1:1. 2) Follow-up period: Assess patients for efficacy endpoints and safety endpoints at 30 days, 90 days and 360 days after randomization.
 

Study treatment	
 
MMA embolization: The surgery is performed under local anesthesia + analgesia, or general anesthesia, and the type of anesthesia is decided by the neurointerventionalists. Different types of catheters are chosen according to patients' anatomy. Arterial access is usually attained via femoral artery groin puncture, however radial or brachial artery access is also allowed. Angiography will usually show MMA dilatation and abnormal vascular staining on the affected side, and then embolic materials are slowly injected into the blood vessels, while avoiding reflux carefully. Investigators who use liquid embolic materials shall be qualified in corresponding training before they can perform the surgery.
 
Drug therapy: Drug treatment can be divided into the symptomatic treatment and treatment promoting hematoma absorption. Indications of drug treatment promoting hematoma absorption: 1) Confirmed diagnosis of non-acute SDH; 2) Patients complicated with multiple organ failure and coagulation dysfunction, etc. who are not suitable for surgery or refuse the surgery; and 3) To prevent postoperative recurrence after
 

Overview of Study Design and Key Characteristics	
	
surgical treatment etc. The contraindications are: allergic to the drug used or having contraindications for the use of the drug.
 
Atorvastatin calcium and dexamethasone are recommended. Atorvastatin calcium with small dose and long course of treatment can be used in combination with dexamethasone. The specific treatment is subject to the local clinical diagnosis and treatment specifications or corresponding clinical guidelines, and is not specified in this study.
 
The application of hemostatic drugs will greatly increase the incidence risk of embolic diseases, so hemostatic drugs are not commonly used.
 
 
• Surgical Treatment: Surgical treatment in this study refers to trepanation and drainage, and local anesthesia + analgesia or general anesthesia can be used for trepanation and drainage.
 
 
Indications of trepanation and drainage: (1) There are clinical symptoms and signs of high intracranial pressure, with or without changes in consciousness and signs of cerebral hemisphere compression; (2) CT or MRI scan shows unilateral or bilateral subdural hematoma with thickness of > 10 mm, and midline shift of > 10 mm due to unilateral hematoma; (3) For those who have been treated with drugs for promoting hematoma absorption for 2 weeks or longer, and whose clinical manifestations and imaging examination have not improved significantly, or whose hematoma continues to increase or medication is intolerable, surgical treatment is recommended.
 
If the subjects in the embolization group need surgery, the embolization will be performed before trepanation and drainage.

Assignment	
 
• Eligible subjects will be randomized 1:1 to either conventional therapy (no MMA embolization) or MMA embolization.
 

Interim Analyses	
 
• The study includes two formal interim analyses, and efficacy analyses will be performed when approximately one-third and two-thirds of patients completed the 90-day follow-up.
 

Sample Size	
 
• 722 cases are expected to be enrolled in this study in China.
 

Study Duration	
 
• In this study, it is estimated that the enrollment time will be from January 2021 to June 2023, that is, the enrolment period will be 30 months from the enrollment of the first subject to the enrollment of the last subject. After the completion of enrollment, the last subject will be followed up to 360 days after randomization.
 

## 2. Statistical Hypothesis

Hypothesis testing will be performed on hematoma recurrence or progression rates.

- Null hypothesis: there is no difference in the incidence of recurrence or progression of hematoma between the MMA embolization group and the control group at 90 days after randomization;

- Alternative hypothesis: there is difference in the incidence of recurrence or progression of hematoma between the MMA embolization group and the control group at 90 days after randomization.

The above hypothesis tests will be two-sided and statistical significance will be determined as a p-value of  $<0.05$ , and two-sided 95% confidence intervals will be reported.

### **3. Sample Size Considerations**

The study hypothesizes that patients undergoing middle meningeal artery embolization may have lower symptomatic recurrence (in the trepanation/drainage group) and lower rates of symptomatic hematoma progression (in the non-surgical group) of subdural hematoma compared to patients who do not go MMA embolization. Two interim analyses will be conducted. With an expected symptomatic recurrence rate (trepanation/drainage group) / symptomatic progression rate (non-surgical group) after MMA embolization of 5% compared with 12% in the control group, and considering a loss to follow-up rate of 8%, a sample size of 722 cases with a two-sided alpha of 0.05 would yield 90% power.

### **4. Planned Analyses**

#### **4.1. Interim Analyses**

Two formal interim analyses was planned to review data relating to treatment efficacy, participant safety and quality of trial conduct using an Haybittle-Peto stopping rule for efficacy. Given the conservative rule used and the negligible amount of type-I error rate spent at the interim analysis, the significance threshold will remain at 5% for the final analysis.

#### **4.2. Final Analysis**

The planned final analysis will be performed after the following steps are completed sequentially:

1. All subjects have completed the study as defined in the protocol.
2. The Statistical Analysis Plan (SAP) has been finalized and approved.
3. All required database cleaning is completed, and the head of Data Management department announces the final database release and database freeze.
4. Randomization codes are issued according to the unblinding process at the end of the trial.

Only blinded data will be reviewed prior to database lock. In addition, no database lock will occur prior to finalization of this SAP.

### **5. Analysis Population**

Population	Definition/Criteria	Analyses Evaluated
All included Subjects Set	
 
• All subjects who signed informed consent.
 
	
 
• Study Population
 

Intent-to-treat Analysis Set (ITT)	
 
• Including all randomized subjects based on the intention-to-treat (ITT) principle, i.e. analysis of subjects based on initial treatment assigned by randomization
 
	
 
• Study Population
 
• Efficacy
 

Per-Protocol Analysis Set (PPS)	
 
• The PPS will include all subjects in the FAS who did not have any major protocol deviations.
 
• Protocol deviations excluding subjects from the PPS are defined in Section 5.1 (Protocol Violations).
 
• Analysis in PPS will be based on the treatment the participant assigned by randomization.
 
• Additional efficacy analyses based on the PPS set will not be performed if the PPS set includes 90% or more of subjects in the FAS and the difference in analysis results between the two analysis sets is expected to be negligible.
 
	
 
• Study Population
 
• Efficacy
 

Safety Set (SS)	
 
• Includes all randomized subjects.
 
• As treated
 
• ITT analysis set
 
	
 
• Safety
 

## 5.1. Protocol Deviations

- Important protocol deviations, including those related to study inclusion/exclusion criteria, trial conduct, subject management, or subject assessment, will be summarized.

- Protocol deviations will be tracked by the study team during the course of the study according to relevant regulations in routine monitoring.
  - All data will be reviewed prior to database lock to ensure that all important protocol deviations and deviations that could lead to exclusion of subjects from the analysis can be captured and classified in the protocol deviation dataset.
  - This dataset will serve as the basis for summaries of protocol deviations.

## 6. Considerations for Data Analyses and Data Handling Conventions

Analyses will be performed using SAS ® System Version 9.4 or higher, and all tables, figures, and listings will be generated as RTF files.

For descriptive statistics, the number of observations (n), standard deviation, median, minimum, maximum, Q1 and Q3 will be presented for continuous variables and number and percentage of subjects will be presented for categorical variables, unless otherwise specified.

Table 2 provides an overview of the appendices in the SAP for outlining general rules for data analyses and data handling conventions.

**Table 2 Overview of Appendix**

Component
Appendix 1: Treatment Period and Study Period
Appendix 2: Data Display Standards and Handling Conventions
Appendix 3: Handling of Premature Withdrawals and Missing Data
Appendix 4: Abbreviations Table

## 7. Study Population Analyses

### 7.1. Overview of Planned Study Population Analyses

Unless otherwise stated, the analyses will be based on the ITT set.

Table 3 provides an overview of the planned study population analyses.

**Table 3 Overview of Planned Study Population Analyses**

	Data Presentation Generated		
	Table	Figure	Listing
Subject Disposition 			
Subjects who entered screening and failed screening			
Randomized Subjects			
Subjects receiving any study treatment			
- Received burr hole drainage			
- Received MMA embolization			
- Received optimal medical therapy			
Completed Subjects	Y		
Subjects who premature withdrew and reasons			
Entered Intent-to-Treat Set (ITT)			
Entered Per-Protocol Analysis Set (PPS)			
Entered Safety Set (SS)			
Protocol Deviations			
Important protocol deviations	Y		Y
Any protocol deviations	Y		Y
Demographic and Baseline Characteristics			
Sex 			
Age (years) 	Y		
Ethnic 			
Weight (kg) 			

	Data Presentation Generated		
	Table	Figure	Listing
Height (m) 			
BMI (kg/m  ) 			
Smoking status 			
Alcohol status 			
Baseline mRS score 			
Prior medical history			
Prior medical history		Y	Y
Prior medication history			
Prior antiplatelet, anticoagulant use			Y
Prior statin use		Y	
Prior hormonal use			
Baseline cranial imaging diagnosis (CT/MRI)			
Massive cerebral infarction 			Y
Intracranial space-occupying lesion 			
Midline shift 			
If yes, shift distance 			
Subdural hematoma 		Y	
If yes, hematoma Side Positions 			
Maximum thickness of hematoma on the enrolled side 			
Volume of hematoma on the enrolled side 			

Notes:

1. Categorized data.

2. Continuous data.
3. Will be based on all screened sets of subjects.

Y = Plan Generation.

## 7.2. Description Of Study Population Analysis

### 7.2.1. Demographic and Baseline Characteristics

- Age (years) will be calculated as (date of informed consent – date of birth)/365.25 rounded down.
- BMI ( $\text{kg}/\text{m}^2$ ) will be calculated as [weight(kg) / (height(cm)/100)  $^2$ ].

## 8. Primary Efficacy Endpoints Analyses

### 8.1. Overview of Planned Primary Efficacy Endpoints Analyses

Unless otherwise stated, the primary efficacy endpoints analysis will be based on the Intent-to-Treat (ITT) and Per-Protocol (PPS) sets. Intent-to-Treat (ITT) set will be the primary analysis set.

Table 4 provides an overview of the planned primary statistical analyses.

**Table 4 Overview of planned primary efficacy endpoints analyses**

	Data Presentation Generated		
	Table	Figure	Listing
Incidence of recurrence (subjects with trepanation) or progression (subjects with no trepanation) of subdural hematoma within 90 days after randomization			
Number and percentage of subjects with event - Hematoma recurrence (in the trepanation/drainage group) in the MMA embolization and control arm respectively - Hematoma progression (in the non-surgical group) in the MMA embolization and control arm respectively - Death within 104 days (90 days + 14 days) in the MMA embolization and control arm respectively	Y		Y
Dichotomous data analyses:			Y

	Data Presentation Generated		
	Table	Figure	Listing

 
- Recurrence (in the trepanation/drainage group)/progression rate (in the non-surgical group) with 95% CI
 
- Difference in recurrence or progression rates between MMA embolization and control groups with 95% CI and CMH Chi-square P value
 
- OR and its 95% CI for the comparison of recurrence or progression rates between treatment and control groups
 
			

## 8.2. Specifications of Primary Efficacy Endpoints Analyses

### 8.2.1. Definitions and Derivations

- **Symptomatic** SDH recurrence (in the trepanation/drainage group) refers to a situation in which the maximum thickness of hematoma of patients exceeds 10 mm, combined with neurological symptoms, or the need for repeat surgery.
- Symptomatic SDH progression (in the non-trepanation/drainage group) refers to a situation in which the maximum thickness of increases by more than 3 mm compared with baseline, combined with neurological symptoms, or the need for surgery.
- The results of central imaging evaluation and analysis of CT/MRI examinations required for the determination of the subject 's primary endpoint in this study will be presented in tables and listings, respectively. Central image evaluation will be performed by the independent Core Lab. Evaluation of neurological symptoms will be derived from the Outcome Assessment Committee (OAC) review data.
- It should be noted that if there is a record of reoperation in participants who have undergone trepanation/drainage, and there is a record of surgical treatment in subjects who have received medical therapy without trepanation/drainage, the occurrence of the primary endpoint can be directly determined, and hematoma thickness or neurological symptoms are no longer required.
- In case of non-negligible amounts of missing data (>5%), we will use the MCMC method based on the Missing at random (MAR) assumption to impute missing data. The regression model will include group, sex, age, BMI, baseline mRS score and baseline maximum

hematoma thickness. The number of imputations is 10, seed=1234, nbiter=200. SAS code examples for multiple imputation will be provided in Appendix 3.

- Hematoma recurrence (trepanation/drainage group) or symptomatic hematoma progression (non-surgical group) at day 90 will be analyzed as follows. If there is any discrepancy between EDC and central imaging assessment scan date in the determination of visit window, the date determined by central imaging assessment shall prevail.

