
- Symptomatic SDH recurrence and progression rate within 90 days post-procedure

Symptomatic SDH recurrence refers to the maximum thickness of hematoma exceeding 10 mm combined with neurological symptoms, or the patient requires re-operation (surgery group);

Symptomatic SDH progression refers to the maximum thickness of hematoma increasing by more than 3 mm compared with baseline, or the patient requires operation (drug therapy group).

Secondary efficacy endpoints:

- Symptomatic SDH recurrence and progression rate at 360 days post-procedure
- Success rate of target vessel embolization (MMA trunk and branch vessels) on digital subtraction angiography (DSA) imaging
- Change in hematoma thickness on computed tomography (CT)/magnetic resonance imaging (MRI) at 90 days post-procedure
- Change in hematoma volume at 90 days post-procedure
- Change in midline shift on CT/MRI imaging at 90 days post-procedure
- Change in mRS score at 90 days and 360 days post-procedure
- Proportion of patients with mRS score ≤ 2 at 90 days and 360 days post-procedure
- Proportion of patients with mRS score ≤ 3 at 90 days and 360 days post-procedure
- Quality of life evaluated with EQ-5D Scale at 90 days and 360 days post-procedure

- Total hospital length of stay, number of re-hospitalizations, discharge location (home vs. rehabilitation hospital), and total hospitalization expenses

The safety endpoints in this study include:

- Serious adverse events (SAEs) within 90 days and 360 days;
- SDH-related mortality within 90 days and 360 days;
- Severe surgery-related complications within 30 days post-procedure (including surgery and embolization)
 - Symptomatic intracranial hemorrhage
 - Surgery-related intracranial hemorrhage
 - Surgery-related neurological deficits
 - Surgery-related central nervous system infection
 - Surgery-related arterial dissection, vascular wall injury, and vascular rupture and perforation
 - Surgery-related ischemia
 - Retroperitoneal/wrist hematoma
 - Neuropathy at the puncture site
 - Contrast allergy or contrast encephalopathy

Note: Follow-up time at 30 days, 90 days, and 360 days post-procedure will be calculated based on the day of randomization in this study. Relevant endpoint events and safety events will be collected at these follow ups.

3. Study Design

[figure not shown]

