7.3 Efficacy Analysis

7.3.1 Primary efficacy analysis

Summarize the incidence of the primary endpoint event.

Primary endpoint event: incidence of recurrence (surgery group) or progression (drug therapy

group) of SDH within 90 days post-procedure

Hematoma recurrence refers that the maximum thickness of hematoma exceeding 10 mm, combined with neurological symptoms, or the patient needs to undergo re-operation (surgery group);

Symptomatic CSDH progression refers that the maximum thickness of hematoma increasing by more than 3 mm compared with baseline, or the patient requires operation (drug therapy group).

Note: The primary endpoint event is considered to have been met for any patient who died from any cause within 90 days post-procedure.

Cochran-Mantel-Haenszel (CMH) chi-square analysis will be used for primary endpoints. The difference in event incidence between the two groups and its 95% confidence interval will be calculated. The Kaplan-Meier (KM) method is further used to estimate the incidence of primary endpoint events and its 95% confidence interval.

SAS code to be used in CMH analysis is as follows:

```
ods output CMH=CMH_out;  
  
proc freq data=FatComp order=data;  
  
tables Layer*Exposure*Response /CMH ALPHA=0.05;  
  
weight count;  
  
output out=cmh_ci cmh;  
  
run;
```

Sas code to be used for KM estimation is as follows:

```
proc lifetest data=TTE alpha=0.05;  
  
time avalm*cnsr(1);  
  
strata /group=trtg;  
  
ods output Quartiles = Quartiles
```

```
ProductLimitEstimates=Estimates;  
run;
```

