## 1. Summary of Protocol

### 1.1. Statistical Analysis Plan and Protocol Discrepancies

All changes to the content of the analyses originally specified in Protocol 3.0 (2022-09-21) are summarized in Table 1.

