**Table 1 Changes to the analysis plan defined in the protocol**

Protocol	Statistical Analysis Plan	
Statistical description in the protocol	Statistical description in statistical analysis plan	Reason for change

 
Section 7.3.1 For the primary endpoint, CMH chi-square analysis will be used to calculate the difference in the event rate between the two groups and its 95% confidence interval, and Kaplan-Meier method will be further used to estimate the event rate of the primary endpoint and its 95% confidence interval.
 
	
 
Section 8.2.2 Primary analysis: 90-day recurrence or progression rates will be summarized for each group using a two-sided 95% CI (Clopper-Pearson method). P-values for differences in recurrence or progression rates between the 2 groups will be compared between groups using the CMH chi-square test. The stratification factor is whether or not trepanation and drainage is performed. In addition, a two-sided 95% CI for the difference in recurrence or progression rates between the two groups will be calculated using the Miettinen-Nurminen method.
 
Sensitivity analysis: Generalized linear mixed-effects model will be used to calculate ORs and their 95% CIs for the comparison of recurrence or progression rates between the two groups for sensitivity analysis with group as a covariate, site as a random
 
	
 
According to internal discussion as well as reference to the design of similar studies, time-to-event analyses were not included for the primary endpoint, and logistic regression analysis methods were added.
 

Protocol	Statistical Analysis Plan	
Statistical description in the protocol	Statistical description in statistical analysis plan	Reason for change
	
effect. Multivariable analysis will also be provided to include group, sex, age, maximum thickness of hematoma on the enrolled side, baseline mRS score.
	

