
 
Section 7.3.2 The analyses of secondary endpoints will be the same as those for the primary endpoint, and comparisons between groups will be made using the Chi-square test (qualitative measure) or t-test (quantitative measure). For event endpoints, the Kaplan Meier method will be used.
 
	
 
For two continuous secondary endpoints, Change of maximum hematoma thickness and hematoma volume between baseline and 90 days, a linear mixed effects model approach will be used to estimate the mean estimate (95% CI) of change from baseline for both treatment groups and mean estimate (95% CI) of difference between groups and p-value of difference between groups; Treatment group variables, sex, age, surgical treatment strata (trepanation/drainage vs. no trepanation/drainage), any usage of antiplatelet or anticoagulant therapy within one month before randomization(yes vs no), hematoma volume of baseline CT will be included in the model. The random effects will be site. For other continuous secondary endpoints, group comparisons will be performed using t-tests or Mann-Whitney U tests and 95% confidence intervals for
 
	
 
According to internal discussion as well as reference to the design of similar studies, secondary endpoints do not include time-to-event analyses and linear mixed effects model analysis methods are added.
 

Protocol	Statistical Analysis Plan	
Statistical description in the protocol	Statistical description in statistical analysis plan	Reason for change
	the difference in means between groups will be calculated using normal approximation.	

 
None
 
	
 
Section 8.2.1 The results of central imaging assessment analysis of CT/MRI examinations required for the determination of the subject's primary endpoint in this study will be presented in tables. Central image evaluation will be performed by the Independent Central Image Review Committee. Neurological symptoms and follow-up mRS scores were derived from OAC review data.
 
Section 9.3.2.1 CEC assessments for adverse events of special interest.
 
	
 
Added central imaging assessments (CT/MRI examinations), CEC assessments (adverse events of special interest), and clarified data sources.
 

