## 1.2. Study Objectives and Endpoints

[figure not shown]
Study objectives	Study Endpoints
Primary objective	Primary Study Endpoints

 
To validate that in patients with symptomatic non-acute subdural hematoma (SDH), MMA embolization with liquid embolic materials can reduce a) the incidence of symptomatic hematoma
 
	
 
Incidence of symptomatic recurrence (in patients who undergo trepanation/drainage) or symptomatic progression of hematoma (in patients who do not undergo trepanation/drainage) within 90 days after randomization
 
Symptomatic hematoma recurrence is defined as maximum hematoma thickness >10 mm in patients in
 

Study objectives	Study Endpoints
recurrence for patients receiving trepanation and drainage and b) the incidence of symptomatic hematoma progression for patients undergoing conservative treatment.	
the trepanation group, combined with neurological symptoms, or that the patient needs to undergo re-operation
 
 
Symptomatic hematoma progression is defined as an increase of >3mm maximum thickness of SDH of patients in the non-trepanation group compared with baseline, or the need for surgery based on the assessment of the treating medical team
 

Secondary objectives	Secondary Study End Point

 
To validate the efficacy of MMA embolization with liquid embolic materials
 
	
 
Incidence of SDH symptomatic recurrence (in patients who undergo trepanation/drainage) and symptomatic progression (in patients who do not undergo trepanation/drainage) 360 days after randomization
 
Success rate of target vessel embolization in DSA imaging
 

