## 9.1.2. Specifications of Secondary Efficacy Endpoint Analyses

### 9.1.2.1. Definitions and Derivations

- Change from 90 days/360 days post study treatment will be calculated as 90 days/360 days measurement – baseline measurement
- Total days in hospital = Date of discharge - Date of hospitalization + 1 (Hospital information page)
- Other definitions and derivations are the same as in Section 8 .2.1

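### SAP 8.2.1 requires neurological symptoms before hematoma growth of more than 3 mm counts as progression; SAP 1.2 and the protocol do not, and SAP Table 1 does not declare the difference

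*SAP*

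**What the plan says.** **Progression, non-trepanation patients.** The endpoint is written in two ways.

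- SAP 8.2.1 sets this condition: "the maximum thickness of increases by more than 3 mm compared with baseline, combined with neurological symptoms, or the need for surgery". A later bullet there lets a record of surgery settle the event without thickness or symptoms, so the symptom condition attaches to growth.
- SAP 1.2 takes an increase above 3 mm and words the rest as "maximum thickness of SDH of patients in the non-trepanation group compared with baseline, or the need for surgery based on the assessment"; the assessor is the treating team. It sets no symptom condition.
- The protocol synopsis and section 2 state: "Symptomatic SDH progression refers to the maximum thickness of hematoma increasing by more than 3 mm compared with baseline, or the patient requires operation".
- Protocol 7.3.1 repeats this rule, again without a symptom condition: "maximum thickness of hematoma increasing by more than 3 mm compared with baseline, or the patient requires operation (drug therapy group").

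For the 360-day endpoint, SAP 9.1.2.1 says: "Other definitions and derivations are the same as in Section 8 .2.1".

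**Declared changes.** SAP 1.1 says: "All changes to the content of the analyses originally specified in Protocol 3.0 (2022-09-21) are summarized in Table 1". The Table 1 row that cites 8.2.1 gives as its reason: "Added central imaging assessments (CT/MRI examinations), CEC assessments (adverse events of special interest), and clarified data sources". The row on protocol 7.3.1 deals with tests, intervals and models.

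**Death.** Protocol 7.3.1 counts death from any cause within 90 days as an event, and protocol section 2 starts the clock at randomization. SAP Tables 4 and 5 and Appendix 3 count death within 104 days (90 + 14), in the primary analysis and in both sensitivity analyses. Table 4 does so under a heading that says 90 days after randomization.

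**The concern.** The two wordings classify the same patient differently. Someone programming the endpoint would work from 8.2.1; someone reading the protocol would expect growth alone to count. No planned analysis shows the result under the other rule, because SAP Table 5 varies only how missing and out-of-window data are treated. Blinded outcome assessment limits bias but does not say which rule applies. If the choice is left until results are known, the primary event count depends on a decision that neither document records.

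**Working it through.** **1. The texts side by side** (unoperated, non-trepanation patient, alive at day 104)

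| Finding by day 90 | SAP 8.2.1 | SAP 1.2 and protocol |
|---|---|---|
| Growth > 3 mm with symptoms | event | event |
| Growth > 3 mm without symptoms | no event | event |
| Growth ≤ 3 mm | no event | no event |

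Only the middle row differs. Operated patients and the recurrence limb are untouched. In the protocol and in SAP 1.2 the recurrence limb carries an explicit symptom clause and the progression limb does not, so the difference lies in the written rule.

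**2. Reproducing the planned size.** Inputs from protocol 7.1.3: 12% v 5%, two-sided 0.05, power 90%, 8% loss; 1:1 allocation. With p̄ = 0.085:

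n = [1.960·√(2·0.085·0.915) + 1.2816·√(0.12·0.88 + 0.05·0.95)]² / 0.07² = (0.7730 + 0.5015)² / 0.0049 = 331.5, so 332 per arm. Then 664 / 0.92 = 721.7, so 722, as stated.

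Power = Φ{[d√n − 1.960√(2p̄q̄)] / √(p₁q₁ + p₂q₂)} with n = 332 gives 90.0%.

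**3. Illustrating the size.** The affected share is not in the documents. I assume that 20-50% of patients are non-trepanation, that 25-50% of their events are symptom-free growth, and that event rates are equal in both strata. The share of all events affected is then 0.20 × 0.25 = 5% up to 0.50 × 0.50 = 25%. Let f = 1 − that share.

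Two things are unknown. One is which definition the 12%/5% describe: protocol 7.1.3 speaks of recurrence or progression, SAP section 3 of symptomatic progression. The other is whether embolization reduces symptom-free growth.

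- Case A: the rates describe growth alone, and the symptom rule is applied. Rates become 12%·f and 5%·f if the treatment effect is proportional. If symptom-free growth has no treatment effect, both fall by 8.5%·(1 − f).
- Case B: the rates describe symptomatic progression, and growth alone is applied. Rates become 12%/f and 5%/f if proportional. If there is no treatment effect, both rise by 8.5%·(1/f − 1).

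Power at 332 per arm:

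| f | A, proportional | A, no effect | B, proportional | B, no effect |
|---|---|---|---|---|
| 0.95 | 88.4% | 91.3% | 91.6% | 88.7% |
| 0.875 | 85.4% | 93.2% | 93.8% | 86.3% |
| 0.825 | 83.1% | 94.4% | 95.1% | 84.5% |
| 0.75 | 79.2% | 96.0% | 96.8% | 81.3% |

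**4. Does the planned effect survive?** Unstratified Pearson chi-square, 332 per arm. As planned, 40 v 17 events, p = 0.001. At f = 0.75, rounded to whole events: A proportional 30 v 13, p = 0.007; A no effect 33 v 10, p = 0.0003; B proportional 53 v 22, p = 0.0001; B no effect 49 v 26, p = 0.005.

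**5. Deaths on days 91-104.** Both documents count from randomization, so the 14 days are not a difference in time origin. Assuming an extra 0.25, 0.5 or 1.0 percentage point in each arm (0.8, 1.7 or 3.3 deaths per arm), power is 89.3%, 88.5% or 86.9%.

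**6. Which protocol version?** The supplied protocol text shows no version number. Table 1 summarizes the protocol as "Section 7.3.1 For the primary endpoint, CMH chi-square analysis will be used to calculate the difference in the event rate between the two groups", which agrees with the supplied 7.3.1. I therefore take the text to be version 3.0.

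**The case against.** The strongest reply is that 8.2.1 only spells out what the endpoint's name already says. Progression is called symptomatic throughout, and on the growth-alone reading that word does no work for this limb. Section 8.2.1 is also where derivations belong, and it gives a usable rule. This stands as a plausible account of intent. It does not remove the conflict with SAP 1.2 or supply the missing Table 1 entry: saying that symptom data come from the Outcome Assessment Committee names a source, not a new condition.

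A second reply is that few patients may be affected. Under protocol 4.1 every patient has neurological symptoms at entry. If symptoms persisting from entry count, the texts differ only for patients whose symptoms cleared while the hematoma grew and no operation followed. This also stands, and the 5-25% range may be too high.

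Third, the version assumption is not secure. Table 1 records nothing in the protocol on central imaging or event-committee assessment, yet protocol 11.5-11.7 describes those committees. That entry may refer only to the statistics section. If the version differs, the undeclared-change part weakens; the conflict between SAP 1.2 and 8.2.1 does not.

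On deaths, day 104 matches the protocol's own 90-day visit window and keeps a patient who dies before an in-window scan from being missing. That is a reasonable motive, but it is not declared.

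**Conclusion.** The point holds as a contradiction in the primary endpoint rule that the SAP does not declare. It should be settled before the endpoint is derived, because the same patient can be an event or a non-event.

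Its numerical weight is uncertain. Under the stated assumptions, power lies between about 79% and 97% around the planned 90%, and the planned effect remains significant in every case tried. The death cut-off is minor: about 87-89% power under the assumed rates.

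A reader might infer three stronger things that the documents do not support:

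- *The symptom rule costs power.* The sign reverses with which definition the 12%/5% describe, and again with whether symptom-free growth responds to treatment. Neither is stated.
- *The choice of rule would decide the trial's significance.* That could be shown only for a hand-picked borderline result, with an affected share that the documents do not give.
- *The sponsor deliberately narrowed the endpoint.* The symptomatic label makes an undeclared clarification at least as plausible.

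**What to change.** Before database lock:

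1. Reconcile SAP 1.2 and 8.2.1 with the protocol to one progression definition. If it departs from the protocol's wording, add a Table 1 row with the reason.
2. Report the primary endpoint under the other definition as a supportive analysis.
3. If symptoms are required for progression, state whether symptoms persisting from entry count. If they must be new or worse, name the source of the baseline comparison: protocol 11.7 specifies committee review of symptoms at least at days 90 and 360, not at baseline.
4. For deaths, choose one of two routes. Either count to day 90 as in the protocol and state how a patient who dies on days 91-104 without a 90-day scan is handled, or declare day 104 in Table 1 and add a day-90 sensitivity analysis.

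The cost is one derivation rule, one or two Table 1 rows and one or two extra tables. All-cause death within 90 days is already tabulated in SAP Table 7.
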